5.2 Laboratory testing

All laboratory results from assays on blood or vaginal swabs, and CVL will be documented on the laboratory results forms (Appendix E).

Specimens collected will be transported within 4 hours to the lab. Blood will be separated and immediately processed for immunophenotyping and immune cell-activation assays, as described below for the vaginal samples. The separated plasma will be aliquoted and stored at -80°C until batch testing commences, as described below for the vaginal samples. Progesterone (P4) and estrogen (E2) levels will be measured in plasma using the Milliplex kit for Luminex Assay (EMD Millipore, Billerica, MA).

A vaginal swab and anal swab will be collected and stored for future microbiome characterization via next-generation sequencing using the Ion Torrent platform to sequence 16S rDNA from bacterial species present in the vaginal compartment.

The CVL specimens will be tested for blood and leukocyte levels with a urine dipstick test and prostate specific antigen (PSA), a marker of semen exposure, using the Abacus ABACard p30 test. The sample will be centrifuged, and the cell pellet will be re-suspended in cell culture media,

Table 5: Summary of Covariates and Analytic Methods for All Specific Aims

Demographics/Behaviors: Questionnaire/Exam: Age, BMI, Race, Parity, Coital frequency

STD Screen: Vaginal swab multiplex PCR for *N.gonorrhoea*, *C. trachomatis*, *T. vaginalis*, *M. genitalium*, *T. pallidum*, HSV-1 & 2. Serum EIA for HIV & HSV. Serum RPR Kit for RPR

Candida vaginitis: Vaginal swab for KOH wet mount examination for hyphae (yeast)

Bacterial Vaginosis: Vaginal swab for gram stain assessment for Nugent score BV diagnosis

Semen: CVL supernatant ABACard® testing for qualitative prostatic specific antigen (PSA)

Serum sex hormones: Serum RIA for E2, P4

Microbiome: Next generation sequencing of 16s rDNA

and the leukocytes will be isolated from epithelial cells using Percoll gradient centrifugation. The resuspended CVL cell pellet (and PBMC pellet, separately) will be split for analysis. One half of the sample will be used for immune cell characterization (i.e., T cell subsets, HIV co-receptor expression) by antibody staining and multi-color flow cytometry using a LSR-2 platform. The other

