half of the sample will be used to assess functional attributes of the T-cells. Cells will be stimulated with PMA and ionomycin (a polyclonal activator) in a tissue culture dish for 5 hours in the presence of brefeldin A and monensin and analyzed for the production of selected cytokines and chemokines by flow cytometry. *Multicolor flow cytometry* will be performed on matched PBMC and CVL samples utilizing the LSR-II platform (BD Biosciences) as previously described.(68) For assessment of HIV target cells, samples will be stained with a Live/Dead viability dye and fluorochrome labeled antibodies against CD3, CD4, CD27, CD45RA, CCR5 and CXCR4. Effector memory (CD45RA-/CD27-) CD3+CD4+ cells will be analyzed for surface expression of HIV co-receptors CCR5 and CXCR4 and reported as percent of total leukocytes and total CD4+ T cells.

We will examine a panel of proinflammatory, anti-inflammatory, inhibitory and chemotactic cytokines and chemokines, focusing our analysis on those previously reported to influence recruitment of HIV target cells to the FRT such as IL1 and IP10(69). Using multiplex Luminex® assays combined with a customized multi-analytical panel of 22 human cytokines and chemokines, we will quantify concentrations of cytokines and chemokines in plasma and CVL supernatant at each study visit from participants enrolled

Recent semen exposure will be measured with a qualitative PSA ABACard® p30 test (Abacus Diagnostics) (70). The wet-mount will be evaluated using saline and 10% KOH for evaluation of budding yeast or hyphae. A gram stain will be performed for Nugent scoring (71) to diagnose BV. A multiplex PCR assay, able to screen for multiple STIs concurrently without the need for multiple samples to be collected, will be used to evaluate for STIs including *N. gonorrhoea*, *C. trachomatis*, *T. vaginalis*, *M. genitalium*, *T. pallidum*, and HSV-1/HSV-2. Serological tests for HIV

and HSV will be performed via enzyme immunoassay (EIA) using a Vitros® 3600 Immunodiagnostic system (Ortho Clinical Diagnostics) and syphilis screening determined via a commercially available rapid plasma reagin (RPR) kit. Positive test results from the research lab can not be relied upon for patient care. Any positive test results concerning for infection from the research lab will trigger further clinical investigation with referral for further testing performed by a CLIA-approved laboratory and treatment.

Table 6. Biological specimens and laboratory methods

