6.5 Limitations and Future Directions

By design the study does not directly address the risk of HIV acquisition from hormonal contraceptives; rather, it explores surrogates that might provide a mechanistic explanation to this purported impact of contraceptive hormone use. Being exploratory in nature, the sample size is small, and we may not be able to detect small differences in some of the outcomes. We have carefully selected our markers to focus on our study aims, however we acknowledge that additional markers may be of interest and can be explored in future evaluations. Additionally, the design is limited by all the inherent biases and confounding associated with a non-randomized, non-blinded study design. Attempts to control for covariates will be performed in the analysis. Further, as our follow-up is limited to 3 months, we cannot evaluate the impact of long-term contraceptive use nor the effect of irregular bleeding on HIV risk. Furthermore, we acknowledge that many other factors that influence HIV susceptibility warrant further investigation, such as epithelial integrity and endogenous microbicides. We plan to use these banked samples to explore some of these other potential mechanisms in future research. The data generated from the successful completion of this study will be instrumental in the design of a future prospective contraceptive trial to explore HIV acquisition risk and to establish safe family planning options for high-risk women.

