Data Management and Statistical Analysis: Study data will be recorded on case report forms and entered into a web-based password-protected relational database (REDCap). Repeated-measures analyses using mixed linear models will be performed with the assistance of Emory CFAR biostatistical core for study endpoints and analyzed with SAS Proc Mixed (version 9) providing separate estimates of the means by contraceptive method and time on study before (weeks 1 and 3) and after (15 and 17 weeks) contraceptive administration. An unstructured variance-covariance form among the repeated measurements will be assumed for each outcome and estimates of the standard errors of parameters will be used to perform statistical tests and construct 95% confidence intervals. The model-based means are unbiased with unbalanced and missing data,

assuming missing data are non-informative and random. Mean changes over time for each contraceptive method will be tested for linear trend. Data will be summarized using adjusted means and observed differences plus 95% confidence intervals. Statistical tests will be 2-sided. A P value ≤ 0.05 will be considered statistically significant.

For multivariable repeated-measures analyses, a mixed linear model will be fit including age, body mass index, race and parity as potential baseline confounders in addition to contraceptive method, time on study and the interaction between time on study and contraceptive method. The multivariable results will be summarized with adjusted means and 95% confidence intervals. The adjusted mean for each contraceptive subgroup (DMPA, Nexplanon, copper IUD and Mirena IUD) will be defined as the mean response obtained by fitting the statistical model at the mean age and the mean BMI of the three subgroups and averaged across levels of the other risk factors. To integrate time-dependent variables, such as BV and PSA, into the longitudinal analyses, each participant at each of the 4 scheduled visits will be classified as positive or negative for each variable. Outcome change will be compared between incident cases and the other women (baseline positive and those that remain negative) after adjusting for the other covariates.

9 Dissemination of Results

The results will be disseminated in the form of abstracts submitted to scientific meetings and manuscripts submitted to peer-reviewed journals.

REFERENCES

1. UNAIDS. UNAIDS Report on the global AIDS epidemic. 2010.

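### The incident-versus-all-others comparison for BV and PSA puts women who may clear into its reference group, and the visits that form the change are not stated

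*Combined protocol and SAP*

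**What the plan says.** Section 8 (Data Management and Statistical Analysis) plans a repeated-measures mixed model with means by method and time, "before (weeks 1 and 3) and after (15 and 17 weeks) contraceptive administration". The multivariable model is described as "including age, body mass index, race and parity as potential baseline confounders in addition to contraceptive method", plus time and the method-by-time interaction.

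BV and PSA are handled in two further sentences. The first states the purpose, "To integrate time-dependent variables, such as BV and PSA, into the longitudinal analyses", and the classification: "each participant at each of the 4 scheduled visits will be classified as positive or negative for each variable". The second gives the only comparison spelled out: "Outcome change will be compared between incident cases and the other women (baseline positive and those that remain negative) after adjusting for the other covariates". The comparator is explicitly one pooled group. Baseline status of the same variable is not among the named adjusters.

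Three other places bear on this:
- Section 4.1.3 excludes only symptomatic vaginal infection at screening, so a woman with asymptomatic BV can enrol.
- Sections 4.3.1, 4.3.2 and 5.1 refer women with infection findings for care. Section 5.1 adds that treatment information beyond standard of care is not recorded.
- Section 5.2 explains what PSA is: "Recent semen exposure will be measured with a qualitative PSA". Its status can therefore change from one visit to the next.

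**The concern.** A comparison meant to show what happens when a woman becomes positive needs a reference group whose status does not change. Here the reference also holds women who start positive. Some may clear between the pre-contraceptive and later visits, and if the marker then falls, their fall is subtracted from the incident women's rise and enlarges the contrast. Others stay positive, and any movement of their own also enters the contrast.

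The second problem is separate. Four visit-level classifications are reduced to one label per woman, and the visits that make up the outcome change are not named. With two visits on each side of contraceptive initiation, a woman positive at only one later visit contributes a full or a half effect depending on a rule the analyst would choose after seeing the data.

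At stake is the reading of the BV and PSA results, and any statement about how much of a marker's change goes with infection or semen exposure.

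**Working it through.** **The plan's own figures.** The documents give no figure for this contrast. The power figures in Section 8 (90% for CCR5, 93% for CD38, 30 per group) reproduce at 90.7% and 93.3% with a two-sided two-sample t-test, but they concern the method comparison.

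**Inputs.** The comparator rule and visit weeks are from Section 8. The CCR5 SD of 17.4 points is also from Section 8. All prevalence, incidence, clearance, reversal and drift values are assumptions shown as ranges.

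**1. Pooling, with status stable within each period.** Let d be the effect of being positive, p baseline prevalence, c the share of baseline positives who clear, r the fraction of d reversed on clearance, and g any extra drift in women who stay positive. Incidence among baseline negatives is 15%. The baseline-positive share of the comparator is w = p / (1 − 0.15(1 − p)). Net of the common time effect, mean changes are d (incident), 0 (never positive), −r·d (cleared) and g (persistent). So

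contrast = d + w·c·r·d − w(1 − c)·g.

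| p | c | r | g | w | contrast |
|---|---|---|---|---|---|
| 0.10 | 0.5 | 1 | 0 | 0.116 | 1.06d |
| 0.30 | 0.5 | 1 | 0 | 0.335 | 1.17d |
| 0.30 | 0.5 | 0.5 | 0 | 0.335 | 1.08d |
| 0.30 | 0.5 | 0 | 0 | 0.335 | 1.00d |
| 0.40 | 1 | 1 | 0 | 0.440 | 1.44d |
| 0.30 | 0 | – | 0.25d | 0.335 | 0.92d |

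Clearance with reversal pushes the contrast up. It falls below d only if (1 − c)·g exceeds c·r·d. With half clearing and full reversal, the drift would have to exceed d itself.

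**2. Which visits form the change (PSA).** Assume positivity q, independent across the four visits, with baseline positive meaning positive at week 1 or week 3. The chance of at least one positive in a two-visit period is B = 1 − (1 − q)². At q = 0.10, B = 0.19. The incident share is 0.81 × 0.19 = 0.1539, so w = 0.19 / 0.8461 = 0.2246. Baseline-positive women change on average by q − q/B = 0.10 − 0.526 = −0.426d.

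- Change averaged over both visits per period: incident women average q/B = 0.526d, so the contrast is 0.526 + 0.2246 × 0.426 = 0.62d.
- Change from week 3 to the later visit at which the incident woman is positive (other women: week 3 to the later visits): incident women change by d, so the contrast is 1 + 0.2246 × 0.426 = 1.10d.

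| q | averaged, pooled | averaged, never-positive reference | week 3 to positive visit, pooled | same, never-positive reference |
|---|---|---|---|---|
| 5% | 0.56d | 0.51d | 1.05d | 1.00d |
| 10% | 0.62d | 0.53d | 1.10d | 1.00d |
| 15% | 0.68d | 0.54d | 1.14d | 1.00d |

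The attenuation follows from averaging, not from pooling: with the never-positive reference it is slightly larger.

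**3. Size against noise.** Take d = 8.7 points (half the CCR5 SD, assumed), p = 0.30 and c = 0.5. The excess is 0.17 × 8.7 = 1.5 points. Incident women number 120 × 0.70 × 0.15 = 12.6 and the others 107.4. With an assumed between-visit correlation of 0.5, the averaged change has SD 17.4 × √0.5 = 12.3, so the standard error is 12.3 × √(1/12.6 + 1/107.4) = 3.7 points.

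**The case against.** The strongest reply is that this analysis is auxiliary. The study is a proof of concept; none of the three aims in Section 3.1 and no power figure uses the contrast. The excess from pooling is well inside its standard error, and every rate behind it is assumed. All of that stands, and it limits the weight of the point.

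Next, the stated purpose of integrating time-dependent variables could mean time-varying covariates. That is possible, but the only comparison written down is a different one.

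The timing is also less open than it may look. Section 8 places weeks 1 and 3 before contraception and the visit schedule in Section 4.1.6 labels both visits pre-contraceptive, so a woman first positive at week 3 is most naturally baseline positive. A reader might infer that incident is wholly undefined; the parenthesis defines it by implication, and only the visit rule is missing.

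For PSA, Sections 4.1.3 and 4.1.6 ask for abstinence (4.1.3 also allows condoms) in the 24 hours before sampling. This should lower positivity but need not abolish it. The averaged-change figures depend on a definition that the documents do not state, and a half effect in a woman positive at one of two visits is partly a choice of estimand. The finding there is the unstated rule, not a demonstrated bias.

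Lastly, a reader might infer that pooling distorts the contraceptive comparison. It does not. Section 6.5 concedes confounding in a non-randomized design and says: "Attempts to control for covariates will be performed in the analysis". If two arms differed in baseline positivity, for example an assumed 40% against 20%, omitting baseline status would shift the difference in change by 0.20 × (c + 0.15)·d. That is 0.13d with half clearing and 0.23d with all clearing, or 1.1 to 2.0 points at d = 8.7, against a standard error of 17.4 × √(2/30) = 4.5. This is a separate, modest matter, and it vanishes if the arms are balanced on baseline status.

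**Conclusion.** The concern holds in a limited form. The stated comparison does not isolate the effect of becoming positive, because its reference group may include women who clear. With reversal on clearance it overstates the effect, by 6% to 44% over the assumed ranges; with no reversal and no drift it is correct. Understatement through pooling needs upward drift in persistent positives.

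For a transient marker the larger uncertainty is the missing definition of change, which moves the PSA result between roughly 0.56–0.68d and 1.05–1.14d. That spread should not be charged to the pooled reference.

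Two stronger readings are not supported. One is that pooling by itself attenuates the PSA result or biases the method comparison. The other, in the plan's favour, is that pooling is harmless when status has no effect: if baseline-positive women drift for unrelated reasons, the contrast is −w(1 − c)·g even with d = 0.

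No aim or power figure is affected. The change is still worth making before analysis, because the plan already collects what the better method needs.

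**What to change.** Replace the incident-versus-other rule with BV and PSA status at each visit as time-varying covariates in the planned mixed model. This uses the classification already planned, drops no women, and removes the questions about week 3 and the change visits.

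If an incidence contrast is kept:
- define baseline positive as positive at week 1 or week 3;
- state which visits form the change;
- use never-positive women as the reference;
- report cleared and persistent women separately.

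The reference group alone is not enough for PSA: with averaged change it still returns only 0.51–0.54d.

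Keep the contraceptive-method model without post-initiation BV as the main result, since Section 2.1 treats a shift towards BV as a possible consequence of progestin exposure and it may lie on the causal path. Present the status-adjusted model as a sensitivity analysis.

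The cost is SAP wording and one extra model, with no new data. The time-varying term assumes one status effect across visits and both within and between women, and this should be stated. At 30% prevalence and 15% incidence, a never-positive reference cuts the comparator from about 107 to 71 women. The standard error rises by about 3%: √[(1/12.6 + 1/71.4) / (1/12.6 + 1/107.4)] = 1.026. Cleared and persistent groups would be small, about 18 each if half clear.
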